5.1 Variables

Plasma concentrations of QCC374 and QCM441 will be expressed in the mass per volume unit ng/mL. The following pharmacokinetic parameters of both analytes (where possible/applicable) will be determined using the actual recorded sampling times and non-compartmental method(s) with Phoenix WinNonlin (Version 6.2 or higher):

- Primary: C_{max}, T_{max}, AUC_{last}, AUC_{tau}, R_{acc} for Day 1 and Day 112
- Secondary: T_{last}, T_{1/2}, T_{min}, C_{min}, fluctuation index, C_{av}, V_z/F (QCC374 only) and CL/F (QCC374 only) for Day 1 and Day 112.

Additional parameters may be determined if appropriate. To denote parameters determined at steady state "ss" will be used. The parameters AUC_{last}, AUC_{tau}, and C_{max} will be converted into molar units using the molecular weight of QCC374 (443.58 g/mol) and QCM441 (415.23 g/mol) to enable the exposure comparison between the two analytes in terms of their ratio QCM441/QCC374.

5.2 Descriptive analyses

QCC374 and QCM441 plasma concentrations will be listed by dose-level, subject, and visit/sampling time point. Missing data will be labeled as such in the concentration data listings. Descriptive summary statistics will be provided by dose-level and visit/sampling time point. Summary statistics will include mean (arithmetic and geometric), SD, CV (arithmetic and geometric), median, minimum and maximum. Concentrations below LLOQ will be treated as zero in summary statistics and for PK parameter calculations. A geometric mean will not be reported if the dataset includes zero values.

Pharmacokinetic parameters for QCC374, QCM441 and their ratio will be listed by dose-level, visit, and subject and summarized by dose-level with descriptive statistics as listed above. Since T_{max} is generally evaluated by a nonparametric method, only median, minimum, and maximum will be reported.

Graphical methods will be employed to show mean and individual concentration-time profiles.

6 Statistical methods for Pharmacodynamic (PD) parameters

All subjects within the PD analysis set will be included in the PD data analysis.

6.1 Secondary objectives

The secondary objective of the study is to assess the treatment effect of QCC374 in PAH patients not previously dosed with QCC374 (Arm 2: those subjects previously in the placebo group).

6.1.1 Variables

The secondary variables are:

- 6MWD
- Right ventricular (RV) function with echocardiography, measured at baseline and at 16 weeks. See Table 6.1 for details.

Table 6-1 Imaging parameters (secondary endpoints)

Imaging parameter (name as in the dataset)	Description	Unit	Directionality
Tvsa	Tricuspid annular peak systolic velocity	cm/sec	Higher is better
tei_index	RV Tei Index	Unitless	Lower is better
Rvfac	RV fractional area change	%	Higher is better
Rvfwls	RV free wall average peak longitudinal strain	%	Lower is better
Tapse	Tricuspid annular plane systolic excursion	cm	Higher is better

The following two definitions of baseline will be used, and where change from baseline will be reported both definitions will be used:

1. Core: Baseline is defined as the Core study (QCC374X2201) baseline visit.
2. Extension: Baseline will be defined as the Extension study (QCC374X2201E1) baseline. The Extension baseline is defined as the Day 112 of the Core study.

6.1.2 Descriptive analyses

The secondary variables (raw values primarily, and change from baseline where needed) will be listed by arm, subject and visit/time and descriptive statistics will be provided by arm and visit/time. Summary statistics will include mean (arithmetic and geometric), SD, CV (arithmetic and geometric), median, minimum, maximum. A geometric mean will not be reported if the dataset includes zero values.

Graphical methods will be employed to show group summary and individual (spaghetti) plots over time by arm as required.

Corporate Confidential Data

7 Statistical methods for safety and tolerability data

All subjects within the Safety analysis set will be included in the safety data analysis.

7.1 Variables

Adverse events, vital signs (blood pressure, pulse rate, body temperature), ECG intervals, laboratory measurements, as well as subject demographics, baseline characteristics, and treatment information.

7.2 Descriptive analyses

Subject demographics and other baseline characteristics

All data for background and demographic variables will be listed by arm and subject. Baseline characteristics will be presented both at Core (QCC374X2201) and Extension study (QCC374X2201E1) baseline. The Extension baseline, is defined, as the Extension study screening visit where the respective measurements are available (as per the assessment schedule) and Day 112 of the Core study where they are not. Summary statistics will be provided by arm.

Relevant medical history, current medical conditions, results of laboratory screens, drug tests and any other relevant information will be listed by treatment group and subject.

Treatment

Data for study drug administration (rescue medication) and concomitant therapies will be listed by arm and subject.

Summary tables will be used to present the proportion of subjects who reached each QCC374 dose, the proportion of subjects who had their dose reduced due to an adverse event, and the proportion of subjects who completed 16 weeks of treatment by dose subject received most from Day 15 to Day 112. Summary statistics for the number of days at each dose will be provided.

Vital signs

All vital signs data will be listed by treatment, subject, and visit/time and if ranges are available abnormalities (and relevant orthostatic changes) will be flagged. Summary statistics will be provided by arm and visit/time.

ECG evaluations

All ECG data will be listed by treatment, subject and visit/time, abnormalities will be flagged. Summary statistics will be provided by arm and visit/time.

Clinical laboratory evaluations

All laboratory data will be listed by treatment, subject, and visit/time and if normal ranges are available abnormalities will be flagged. A separate listing is provided presenting all parameters in a subject with any abnormal values. Summary statistics will be provided by arm and visit/time.

Adverse events

All information obtained on adverse events will be displayed by arm and subject.

The number and percentage of subjects with adverse events will be tabulated by body system and preferred term with a breakdown by arm. A subject with multiple adverse events within a body system is only counted once towards the total of this body system and arm.

For the legal requirements of ClinicalTrials.gov and EudraCT, two required tables on treatment emergent adverse events which are not serious adverse events with an incidence greater than 5% and on treatment emergent serious adverse events and SAE suspected to be related to study treatment will be provided by system organ class and preferred term on the safety set population.

If for a same patient, several consecutive AEs (irrespective of study treatment causality, seriousness and severity) occurred with the same SOC and PT:

- a single occurrence will be counted if there is ≤ 1 day gap between the end date of the preceding AE and the start date of the consecutive AE
- more than one occurrence will be counted if there is > 1 day gap between the end date of the preceding AE and the start date of the consecutive AE.

For occurrence, the presence of at least one SAE / SAE suspected to be related to study treatment / non SAE has to be checked in a block e.g., among AE's in a ≤ 1 day gap block, if at least one SAE is occurring, then one occurrence is calculated for that SAE.

The number of deaths resulting from SAEs suspected to be related to study treatment and SAEs irrespective of study treatment relationship will be provided by SOC and PT.

Other safety evaluations

Spirometry

All spirometry data will be listed by subject and visit/time. Summary statistics (raw values primarily, and change from baseline) will be provided by QCC374X2201 study arm and visit/time.

Baseline is defined as the Day 112 of the Core study for the subjects who received QCC374 in the Core study, and the Screening visit of the Extension study for the subjects who received placebo in the Core study.

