Enrollment	Point/time of subject entry into the study at which informed consent must be obtained (i.e. prior to starting any of the procedures described in the protocol)
Epoch	Interval of time in the planned conduct of a study. An epoch is associated with a purpose (e.g. screening, randomization, treatment, follow-up), which applies across all arms of a study.
Healthy volunteer	A person with no known significant health problems who volunteers to be a study participant
Investigational drug	The study drug whose properties are being tested in the study; this definition is consistent with US CFR 21 Section 312.3 and Directive 2001/20/EC and is synonymous with “investigational new drug” or “test substance”
Investigational treatment	All investigational drug(s) whose properties are being tested in the study as well as their associated treatment controls. This includes any placebos, any active controls, as well as approved drugs used outside of their indication/approved dosage or tested in a fixed combination. Investigational treatment generally does not include other treatments administered as concomitant background therapy required or allowed by the protocol when used within approved indication/dosage.
Medication number	A unique identifier on the label of each study drug package in studies that dispense study drug using an IRT system.
Medication pack number	A unique identifier on the label of each drug package in studies that dispense study treatment using an IRT system
Non-investigational medicinal Product (NIMP)	Products which are not the object of investigation (e.g. any background therapy administered to each of the clinical trial subjects, regardless of randomization group, rescue medication, active drug run-ins etc.)
Part	A single component of a study which contains different objectives or populations within that single study. Common parts within a study are: a single dose part and a multiple dose part, or a part in patients with established disease and in those with newly-diagnosed disease.
Patient	An individual with the condition of interest

Period	A minor subdivision of the study timeline; divides phases into smaller functional segments such as screening, baseline, titration, washout, etc.
Premature subject withdrawal	Point/time when the subject exits from the study prior to the planned completion of all study drug administration and assessments; at this time all study drug administration is discontinued and no further assessments are planned.

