3.2 Rationale of study design

This open-label safety extension study will offer continuous QCC374 therapy to PAH patients who have completed the study QCC374X2201, and will provide long-term safety, tolerability and efficacy data.

- **Open-label:** This is a long-term study designed to assess safety and all subjects will receive active treatment
- **Dose-titration design:** This applies only to subjects in Arm 2 (i.e. those who are initiating treatment with QCC374 at the beginning of the study). All current marketed prostacyclins have an up-titration dosing strategy to increase prostacyclin tolerability. With up-titration significantly higher prostacyclin doses can be tolerated as compared to single dose administration
- **Starting dose:** This applies only to subjects in Arm 2 (i.e. those who are initiating treatment with QCC374 at the beginning of the study). The starting dose in Arm 2 is 0.03 mg, which is the same as the starting dose in the QCC374X2201 study.
- **Eligibility:** All subjects who completed QCC374X2201 are eligible to enroll. At the time of enrollment the efficacy of QCC374 in PAH patients will be unknown, as efficacy data from QCC374X2201 will not yet be available. All subjects who completed QCC374X2201 are eligible to enroll in the extension study in order to avoid an interruption in prostacyclin therapy.
- **Endpoints:** The primary endpoint of this study is the number of participants with adverse events as a measure of safety and tolerability. In addition, there are secondary

Corporate Confidential Information

Together these assessments are anticipated to inform future, larger studies of QCC374 in PAH.

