7.3 Withdrawal of informed consent

Subjects may voluntarily withdraw consent to participate in the study for any reason at any time. Withdrawal of consent occurs only when a subject:

- Does not want to participate in the study anymore, and
- Does not allow further collection of personal data

In this situation, the investigator should make a reasonable effort (e.g. telephone, e-mail, letter) to understand the primary reason for the subject's decision to withdraw his/her consent and record this information.

Study treatment must be discontinued and no further assessments conducted, and the data that would have been collected at subsequent visits will be considered missing.

Further attempts to contact the subject are not allowed unless safety findings require communicating or follow-up.

All efforts should be made to complete the assessments prior to study withdrawal. A final evaluation at the time of the subject's study withdrawal should be made as detailed in the assessment table.

Novartis will continue to keep and use collected study information (including any data resulting from the analysis of a subject's samples until their time of withdrawal) according to applicable law.

For US: All biological samples not yet analyzed at the time of withdrawal may still be used for further testing/analysis in accordance with the terms of this protocol and of the informed consent form.

For EU and ROW: All biological samples not yet analyzed at the time of withdrawal will no longer be used, unless permitted by applicable law. They will be stored according to applicable legal requirements.

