7.6 Early study termination by the sponsor

The study can be terminated by Novartis at any time for any reason. This may include reasons related to the benefit/ risk assessment of participating in the study, practical reasons (including slow enrollment), or for regulatory or medical reasons. Should this be necessary, subjects must be seen as soon as possible and treated as a prematurely withdrawn subject. The investigator may be informed of additional procedures to be followed in order to ensure that adequate consideration is given to the protection of the subject's interests. The investigator will be responsible for informing IRBs/IECs of the early termination of the trial.

Epoch	Extension-Treatment ^{5,6}						
Visit Name	EOS (30 days post last treatment)						
Visit Numbers ¹	427	428	429	430	431	432	433 ⁵
Study Day(s)	570 ±5	600 ±5	630 ±5	660 ±5	690 ±5	720 ±5	750 ±5
Time (post-dose)	-	-	-	-	-	-	-
Informed consent							
Inclusion / Exclusion criteria							
Physical examination			X			X	X
Pulse oximetry			X			X	X
Vital Signs			X			X	X
Pregnancy test			X ³			X ³	X ³
Body weight							X
Blood chemistry			X			X	X
Hematology			X			X	X
Urinalysis			X			X	X
Spirometry			X			X	X
ECG evaluation			X			X	X
6-Minute Walk Test			X			X	X
			X			X	
			X			X	
						X	
						X	
Corporate Confidential Information						X	
						X	
Echocardiogram							
Corporate Confidential Information	X						
Drug dispensation	X	X	X	X	X	X	
Study drug administration	Study drug administration will be bid - refer to Section 3.1 and Site Operational Manual						

Epoch	Extension-Treatment ^{5,6}						
Visit Name							EOS (30 days post last treatment)
Visit Numbers ¹	427	428	429	430	431	432	433 ⁵
Study Day(s)	570 ±5	600 ±5	630 ±5	660 ±5	690 ±5	720 ±5	750 ±5
Time (post-dose)	-	-	-	-	-	-	-
Concomitant medications	As Required						
Adverse events	As Required						
Serious adverse events	As Required						
Comments	As Required						
Study/epoch completion information							X

¹ Visit structure given for internal programming purpose only

² The earliest that informed consent can occur is Day 111 in the companion QCC374X2201 study, and informed consent can occur no later than 7 days after Day 111.

³ Urine Pregnancy Test (females only)

⁴ The first drug study dispensation may occur on Day -1 or Day 1.

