10.5 Adjudication Committee

Not required

11 Data analysis

The analysis will be conducted on all subject data at the time the trial ends. Any data analysis carried out independently by the investigator should be submitted to Novartis before publication or presentation.

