11.4.3 Handling of missing values/censoring/discontinuations

All patients who received study drug will be included in the safety and tolerability evaluation.

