1.3 Study objectives

1.3.1. Primary objective(s)

Primary objective(s)	Endpoints related to primary objectives

 To evaluate the safety and tolerability of QCC374 in patients with PAH over a two year period 	
 Adverse Events, Serious Adverse Events and all safety assessments

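### The AE tables give counts and percentages without observation time, so if follow-up is cut short they understate two-year risk without showing it

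*SAP*

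**What the plan says.** SAP 1.3.1 gives the primary objective as: "To evaluate the safety and tolerability of QCC374 in patients with PAH over a two year period". Protocol 3.1.1.2 plans 720 days of treatment in both arms. Protocol 3.2 makes the endpoint a count: "The primary endpoint of this study is the number of participants with adverse events as a measure of safety and tolerability".

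The main AE table in SAP 7.2 follows that endpoint: "The number and percentage of subjects with adverse events will be tabulated by body system and preferred term with a breakdown by arm". Protocol 11.4.2 and 11.4.4 describe the same table, and the first interpretable results (SAP 2) include n (%) by body system. The registry tables in SAP 7.2 add counts of occurrences and deaths. None of these has a time denominator.

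The protocol section on missing values, censoring and discontinuations (11.4.3) consists of one inclusion rule: "All patients who received study drug will be included in the safety and tolerability evaluation".

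Two provisions can end follow-up before Day 720:
- **Sponsor termination (Protocol 7.6):** "subjects must be seen as soon as possible and treated as a prematurely withdrawn subject". The glossary says of premature withdrawal that "at this time all study drug administration is discontinued and no further assessments are planned". Protocol 11 then says: "The analysis will be conducted on all subject data at the time the trial ends".
- **Withdrawal of consent (Protocol 7.3):** "no further assessments conducted, and the data that would have been collected at subsequent visits will be considered missing".

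Some exposure information is planned: subject disposition (SAP 2), and days at each dose plus listings of drug administration and AEs by arm and subject (SAP 7.2).

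**The concern.** A percentage of subjects with an AE can be read as a two-year risk only if most subjects were observed for about two years. Here every dosed subject stays in the denominator, however briefly observed, and no visible rule deals with unequal follow-up. If follow-up ends early for reasons unrelated to AEs, some first events fall after observation has stopped, and the percentage comes out too low. The error then runs one way, towards a safer-looking drug.

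The AE table gives no warning, because the same n (%) can rest on very different amounts of observation. Disposition, days at each dose and the listings help only in part. They are not tied to the AE table, and time on drug by dose level is not the same as time under AE observation. Protocol 7.1 also defines completion by voluntary withdrawal or sponsor termination rather than by reaching Day 720, and the only completion proportion described in SAP 7.2 is for 16 weeks.

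**Working it through.** The plan has no figure to reproduce: Protocol 11.7 gives no sample size calculation, 11.4.2 rules out inference, and no AE or dropout rate is stated for the extension. What follows is illustration.

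**Inputs**
- Horizon: 720 days (Protocol 3.1.1.2), T = 720/365.25 = 1.971 years.
- Subjects: about 30, the expected Core completers (Protocol synopsis), all expected to roll over (Protocol 4). Fifteen per arm is an assumption.
- True 720-day risk p: assumed 50%, with 20% and 80% as a range.
- Loss L by Day 720: assumed 10%, 21%, 40% and 60%. The 21% is the Core planning figure, (38 − 30)/38, borrowed only as a reference point.

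**Formulas (constant hazards, dropout unrelated to AEs)**
- AE hazard λ = −ln(1 − p)/T; for p = 0.5, λ = 0.3516 per year.
- Dropout hazard δ = −ln(1 − L)/T; 0.1196 at 21%, 0.2591 at 40%.
- Expected crude proportion = λ/(λ + δ) × [1 − (1 − p)(1 − L)].
- At 21% loss: 0.3516/0.4712 × (1 − 0.5 × 0.79) = 0.451.
- At 40% loss: 0.3516/0.6107 × (1 − 0.5 × 0.60) = 0.403.
- All follow-up stopped at Day 360: 1 − 0.5^(360/720) = 0.293.

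**Variants**
- Front-loaded: hazard 4λ to Day 112, then λ, with λ = −ln(1 − p)/(4t₁ + T − t₁) and t₁ = 112/365.25.
- Partly AE-driven dropout: only half of δ acts before a first AE.

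Expected crude percentage:

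| Scenario | 10% loss | 21% | 40% | 60% | Stop at Day 360 |
|---|---|---|---|---|---|
| Risk 50%, constant | 47.7 | 45.1 | 40.3 | 34.5 | 29.3 |
| Risk 50%, front-loaded | 48.4 | 46.6 | 43.2 | 39.0 | 36.7 |
| Risk 50%, half of δ before first AE | 48.9 | 47.5 | 44.8 | 41.2 | – |
| Risk 20%, constant | 19.0 | 17.9 | 15.8 | 13.3 | 10.6 |
| Risk 80%, constant | 77.0 | 73.4 | 66.8 | 58.6 | 55.3 |

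If all dropout follows an AE already counted, there is no understatement.

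**Against sampling error.** With 15 subjects the SE of a 50% proportion is √(0.5 × 0.5/15) = 12.9 points. The shortfall is 4.9 points at 21% loss, 9.7 at 40% and 20.7 for the Day 360 stop. It reaches one SE at about 51% loss (68% if front-loaded), or if all follow-up stops at about Day 481 (Day 370 if front-loaded).

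**What the table hides.** Follow-up for 15 subjects is 15 × 1.971 = 29.6 patient-years if complete, 15 × 0.40/0.2591 = 23.2 at 40% loss, and 15 × 360/365.25 = 14.8 if stopped at Day 360. Zero events among 30 subjects gives a one-sided 95% upper limit of 1 − 0.05^(1/30) = 9.5% at any length of follow-up. As a rate, −ln(0.05)/patient-years, the limit is 5.1 per 100 patient-years at 720 days (59.1 patient-years) but 20.3 at 180 days (14.8 patient-years).

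**The case against.** The strongest reply is that the plan delivers its own endpoint. Protocol 3.2 asks for the number of participants with AEs, and that is what is tabulated, descriptively and without inference. No passage sets cumulative risk to Day 720 as the target, and the two-year wording could simply describe the planned span of observation. This stands in part: the table is not wrong for its endpoint. It does not, by itself, support a statement about two years.

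Second, nothing predicts heavy loss. Protocol 7.2 and 7.4 keep subjects in the study after stopping drug unless they withdraw consent. Protocol 3.1.1.3 and the footnotes to the assessment schedules ask for at least a safety evaluation after a premature stop. Protocol 7.6 is a general right to terminate, not a forecast. This stands, and it is why the point is conditional.

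Third, the shortfall is below one SE in most illustrated cases, and the prostacyclin-type AEs the protocol expects may come early. This also stands, but a one-directional error is not removed by being smaller than the noise.

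Fourth, time on drug can be derived from the listings for about 30 subjects. This is largely true, but observation time off drug is less clear, and nobody reading the AE table alone would see either.

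A reader might go further and infer that exposure is not reported at all, or that the arm columns amount to a misleading comparison. The documents do not support either. Days at each dose are summarised, the protocol labels the columns by Core treatment, and no comparison is planned.

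**Conclusion.** The point holds in a conditional form. The visible AE summaries have no time base although the objective covers two years, and the plan permits follow-up to end early. If that happens materially and for reasons unrelated to AEs, the crude percentage understates two-year risk and the AE table does not reveal it. For a true risk of 50%, the illustrated shortfall runs from about 2 points at 10% loss to about 21 points for a stop at Day 360 under a constant hazard. It is smaller if events are front-loaded, and absent if dropout follows AEs already counted. These sizes rest on assumed risks, hazards and losses, since the documents supply none for the extension.

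A reader might infer that the planned percentages will be seriously biased, or that the primary endpoint is not analysed. Neither follows: no heavy loss is forecast, and the endpoint is delivered as stated. The weakness is one of interpretability and is cheap to repair. Table shells and redacted text were not available, and they may already hold exposure outputs.

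**What to change.** In SAP 7.2, keep the n (%) tables and add, labelled as descriptive:

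1. Patient-years of AE observation per arm, printed beside the AE tables, with the start and end of the at-risk window stated.
2. Subjects with a first event per 100 patient-years at risk, with exact 95% CI, for any AE, SAEs, and AEs leading to discontinuation. Each subject's time at risk runs to the first event or the end of the window.

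Optionally, split these outputs at 16 weeks of extension time, which eases the constant-hazard assumption.

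**Cost.** A few extra descriptive tables for about 30 subjects. AE start and end dates (Protocol 9.1) and drug administration data (SAP 7.2) are already collected.

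**Downsides.** Intervals will be wide: 7 first events in 20 patient-years is 35 per 100, with exact 95% CI from χ²(0.025; 14)/(2 × 20) to χ²(0.975; 16)/(2 × 20), that is 14 to 72 per 100. A single rate also assumes a roughly constant hazard over the period it covers. If the table shells already contain these outputs, a cross-reference in SAP 7.2 is enough.
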